3.5.4. Step 3: Compute Boundary Values for Primary Outcome

Boundary values for the primary outcome will be derived via the SEQDESIGN (REF SAS SEQDESIGN) procedure in SAS; specifically using a two-sided O’Brien Fleming design which has conservative stopping boundary values at early stages, and boundary values at the final stage that are close to the fixed-sample design. This produces a conservative design because compared to other approaches, the O’Brien-Fleming approach makes it more difficult to reject the null hypothesis in early stages than in later stages (null hypothesis being that there is no difference in 30-day HF-related direct medical costs between the Furoscix Infusor and historical control arms).

Assume that the total 30-day HF-related direct medical costs are normally distributed with means μ_e and μ_c for individuals in the Furoscix Infusor and historical control groups, respectively. The null hypothesis of no effect for the Furoscix Infusor is $H_0 : \theta = 0$, where $\theta = \mu_e - \mu_c$

The specific procedure for determining the boundary values for the primary outcome are specified elsewhere (REF SAS SEQDESIGN). Utilizing this procedure requires that we prespecify the meaningful difference between groups and the standard deviation thereof in order to achieve the specified power. The boundary values will be estimated based on a difference of \$2,100 (based an average hospital cost of a patient hospitalized for ≤ 72 hours with a primary diagnosis of HF (Diagnosis Related Group Code 291, 292 and 293) of \$8,600 (standard deviation: \$3,045), 68 patients (34 in each group) are required to have an 80% chance of detecting a decrease in hospital costs to \$6,500 at a significance level of 5%).

3.5.5. Step 4: Interim and Final Analysis with Propensity Match

Interim analyses to determine whether efficacy or futility has been reached will be conducted in a prespecified manner at N=10 and N=34 in the evaluable population. Additional interim analyses may be conducted as needed. Note that the enrollment for the prospective arm will continue as the interim analysis is carried out up to N=34, at which point re-assessment of sample size will be conducted.

For the interim analyses, the comparators will be historical controls drawn from the aforementioned candidate pool using a 1:1 to 4:1 propensity score matched approach. The propensity score matching process will be conducted via a caliper-based mechanism that allows for an iterative matching approach that will maximize the efficiency of the match protocol using methods reported by Millar and Pasta 2010.

The primary final analysis will include a 1:1 to 4:1 propensity match using the identical algorithm produced in the last interim analysis. Additional final analyses will explore the impact of increasing the ratio of cases to controls up to a 1:10 match. Note that the aforementioned matching method will be applied so that no Furoscix subjects will be dropped from the analysis due to the lack of a suitable match or matches.

The propensity scores (1 for each case and control) will be generated with the SAS PROC LOGISTIC function to produce a multivariate logistic regression. The propensity score is the predicted probability of receiving the Furoscix Infusor treatment. Both automatic stepwise and manual variable selection will be evaluated.

Criteria for propensity score matching are listed below:

- In addition to requiring that the absolute difference between the treatment arm propensity score and the control patient's propensity score be no larger than 0.01, exact sex, the absolute difference in age could be no larger than 5 years, and time between time zero visits could be no more than 730 days (or 1095 days). These key measure requirements reduced the data set substantially to a data set of potential matches.
- A logistic regression model will be developed to estimate a propensity score for each subject. The model will include candidate variables (defined in Section 3.5.2 Step 2: Produce Candidate Pool for Historical Cohort). The dependent variable will be binary and indicate either prospective patient or historical control patient. Backwards stepwise selection will be implemented with alpha level of 0.1 or 0.20 to identify predictor variables of receiving Furoscix (prospective subject vs. historical control). The final model including candidate variables identified from backwards stepwise selection will be used to generate a predicated probability (propensity score of receiving Furoscix) for each subject.
- For treatment arm, the variables will be defined at time zero (enrollment/ED visit); for control patients, the variables will be defined at index as a possible match.
- Once final matches are identified, to assess balance in confounding variables between cases and controls, for each of the candidate variables included in the propensity score modeling, effect sizes (normalized difference between cases and controls) will be calculated based on the differences between the matched pairs. An effect size of <0.20 will be deemed acceptable.
- Control patients' data were weighted based on the number of controls within each matched treatment arm patient set. For instance, if a control patient was part of a set with 1 other control patient, each control patient in that set was weighted 0.50 (1 divided by the set count 2).
- In addition to the effect size evaluation, the baseline characteristics, i.e. all initial candidate variables for propensity model, between the two cohorts will be compared statistically and any variable difference with a p value of <0.1 will be identified.

Analyses, whether they be interim or final, will be conducted sequentially using the SEQTEST procedure in SAS, which has been specified elsewhere (SAS Institute, 2009). Briefly, The SEQTEST procedure performs interim and final

analyses by comparing test statistics with corresponding boundary values obtained with the SEQDESIGN procedure. If the information levels for the test statistics do not match the information levels obtained with the SEQDESIGN procedure, the SEQTEST procedure modifies the original boundary values to adjust for actual (observed) information levels.

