8. STATISTICS

8.1. Determination of Sample Size

Based on an average hospital cost of a patient hospitalized for \leq 72 hours with a primary diagnosis of HF (Diagnosis Related Group Code 291, 292 and 293) of \$8,600 (standard deviation: \$3,045), 68 patients (34 in each group) are required to have an 80% chance of detecting a decrease in hospital costs to \$6,500 at a significance level of 5%. The target sample size of the Furoscix cohort will initially be N=34 subjects.

Given the anticipated overdispersion of the primary outcome (i.e., difference in total HF-attributable direct medical costs), we will employ adaptive trial design procedures for sample size re-estimation. This adaptive-total information criterion approach was taken due to the risk of incorrectly estimating the sample size due to misspecification of the cost outcome parameters. By using the adaptive sample size design, which includes no penalty for repeated interim analysis, the final sample size will be sufficient to provide adequate power to test the stated hypothesis.

This will include re-assessment of the sample size at N=34 in the Furoscix cohort by using a group sequential design and testing to allow for stopping. It is not expected that the sample size for the Furoscix Infusor arm would exceed N=75, but the maximum value cannot be definitively stated until the analysis at N=34 is completed.

We will explore ratios ranging from 1:1 to 4:1 for the number of historical controls to be matched to Furoscix-treated patients using methods reported by Millar and Pasta 2010. The simulations will be used to find the matching ratio at which the level of precision is optimized without biasing the variance of the outcome measure. Additional methodological details are described in the prespecified statistical analysis plan.

The methodology by which the sample size will be re-estimated and stopping rules will be implemented will be detailed in the statistical analysis plan.

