3.3.3. P-Values

The statistical test for the primary objective will be performed at two-sided $\alpha=0.05$. All reported p-values ≥ 0.0001 will be rounded to four decimal places. P-values <0.0001 will be displayed as “ <0.0001 ”.

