The four stages of the hypothetical trial presented in the preceding figure are indicated by vertical lines labeled 1, 2, 3, and 4. With early stopping to reject the null hypothesis, the lower rejection boundary is constructed by connecting the lower critical values for the stages. Similarly, the upper rejection boundary is constructed by connecting the upper critical values for the stages. The horizontal axis indicates the sample size for the group sequential trial, and the vertical axis indicates the values of the test statistic on the standardized Z scale. At each interim stage, if the test statistic falls into a rejection region the trial stops and the null hypothesis is rejected. Otherwise, the trial continues to the next stage. At the final stage the null hypothesis is rejected if Z falls into the rejection region. Otherwise, the null hypothesis is not rejected. In the figure, the test statistic falls into the rejection region in stage 3 and the null hypothesis is rejected.

An important concern with group sequential designs is correcting for multiplicity caused by conducting multiple, sequential correlated statistical tests thereby increasing the probability of Type 1 error. To correct for this issue one must preemptively define local significance levels for each statistical test and define the stopping boundaries. Herein, we will employ the O'Brien and Fleming error spending function to distribute the overall Type 1 error rate across the interim and final analyses. Because the O'Brien and Fleming approach includes an increase in the local significance level with each subsequent analysis (i.e., with each stage) it is considered among the more conservative approaches.

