3.5.2. Step 1: Determining the Initial Target Sample Size

Although this is an adaptive clinical trial with sequential cohort design whereby the final sample size will ultimately be determined by the prespecified interim analyses, it was necessary for trial planning purposes to generate an estimated final sample size based purely on a priori assumptions.

Based on an average hospital cost of a patient hospitalized for \leq 72 hours with a primary diagnosis of HF (Diagnosis Related Group Code 291, 292 and 293) of \$8,600 (standard deviation: \$3,045), 68 patients (34 evaluable patients in each group) are required to have an 80% chance of detecting a decrease in hospital costs to \$6,500 at a significance level of 5%. The target sample size of the Furoscix cohort will initially be N=34 subjects.

Re-assessment of the sample size will be conducted once 34 subjects in the Furoscix cohort complete all study phases as per protocol (matched 1:1 to 4:1 to propensity matched controls to generate comparisons) by using a group sequential design and testing to allow for stopping. It is not expected that the sample size for the Furoscix Infusor arm would exceed N=75, but the maximum value cannot be definitively stated until the analysis at N=34 is completed.

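### The SAP states no small-sample conversion before test statistics meet normal-theory O'Brien-Fleming boundaries; on the t-test branch the two-sided error is then about 5.2% to 6.2%, not 5%

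*SAP*

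**What the plan says.** **Error rate and test.** SAP 3.3.3: "The statistical test for the primary objective will be performed at two-sided" alpha of 0.05. SAP 3.5.1 and Protocol 8.3.1 allow a t-test or a Wilcoxon signed-rank test on the matched cohorts, chosen by the distribution of the data.

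**Boundaries.** SAP 3.5.4 takes them from a two-sided O'Brien-Fleming design in SEQDESIGN and assumes normally distributed costs. SAP 3.3.5 speaks of an O'Brien-Fleming error spending function. Explaining a hypothetical four-stage figure, it says that "the vertical axis indicates the values of the test statistic on the standardized Z scale".

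**Comparison rule.** SAP 3.5.5 says that SEQTEST works by "comparing test statistics with corresponding boundary values obtained with the SEQDESIGN procedure". The only adjustment it describes is for information levels that differ from plan. Degrees of freedom, a t reference distribution and p-value conversion are not mentioned.

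**Looks.** SAP 3.5.5 says that analyses to decide whether "efficacy or futility has been reached will be conducted in a prespecified manner at N=10 and N=34 in the evaluable population". It calls both interim and permits more as needed. SAP 3.5.2 expects no more than 75 Furoscix subjects but fixes no maximum. Protocol 8.1 names only N=34, for "re-assessment of the sample size at N=34 in the Furoscix cohort by using a group sequential design and testing", and leaves stopping methods to the SAP.

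**The concern.** A boundary of 1.96, or of 3.6 at an early look, has its intended tail probability only for a statistic that is normal under the null. A t statistic from 10 pairs has 9 degrees of freedom, and one from 34 pairs has 33. Both have heavier tails than the normal, so the same cut-off is crossed too often by chance. If the analyst feeds the t statistic to the boundary unchanged, the 5% in SAP 3.3.3 is missed even when every planned look is followed exactly. The rule that stops the trial and declares a cost difference is then looser than stated.

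**Working it through.** **Inputs.** Two-sided alpha 0.05 (SAP 3.3.3). Group size and power: "68 patients (34 evaluable patients in each group) are required to have an 80% chance of detecting a decrease in hospital costs to" $6,500 (SAP 3.5.2). Control mean $8,600, "standard deviation: \$3,045". SAP 3.5.4: "The boundary values will be estimated based on a difference of" $2,100. Looks at 10 and 34; expected ceiling 75.

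**Step 1: reproduce the plan's sample size.** Standardised effect = 2,100 / 3,045 = 0.690. n per group = 2(1.960 + 0.842)² / 0.690² = 33.0, rounded up to 34. Two-sample noncentral t power at 34 per group is 80.0%. The plan's figure is reproduced.

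**Step 2: boundaries for looks at 10 and 34, with 34 last.** Information fraction t = 10/34 = 0.294, √t = 0.542.
- Classical O'Brien-Fleming: c/√t with c = 1.961, giving 3.616 and 1.961. Nominal two-sided p at N=10 is 0.0003.
- Error spending: 4[1 − Φ(2.241/0.542)] = 0.00007 spent at N=10, giving 3.971 and 1.960.

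**Step 3: true tails of an unconverted paired t.**
- N=10, 9 df: 2P(T > 3.616) = 0.0056, and 2P(T > 3.971) = 0.0032. Intended: 0.0003 and 0.00007.
- N=34, 33 df: 2P(T > 1.96) = 0.058. Intended: 0.050.

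**Step 4: overall type I error.** Simulated with normal data, at least 200,000 trials per cell; repeat runs agree to about 0.1 point.

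| Looks | Boundary type | Paired t | Two-sample t |
|---|---|---|---|
| 10, 34 | classical | 6.2% | 5.6% |
| 10, 34 | error spending | 6.0% | 5.5% |
| 10, 34, 75 | classical | 5.6% | 5.3% |
| 10, 34, 75 | error spending | 5.5% | 5.2% |

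Paired t, classical, with other final sizes: 6.2% at 40, 6.0% at 50, 5.8% at 60. As the final N grows, the N=10 boundary rises (5.40 for a final N of 75) and its false-stop rate falls to 0.04%.

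**Step 5: source of the excess.** In the worst case the excess is 6.2 − 5.0 = 1.2 points. N=34 alone against 1.96 gives 5.8%, an excess of 0.8. About two-thirds therefore arises without the 10-pair look.

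**Step 6: signed-rank branch.** For symmetric differences the 10/34 error is 4.8%. With 10 pairs the largest possible Z is (55 − 27.5)/√(10·11·21/24) = 2.80, below 3.616. The smallest exact two-sided p is 2/2¹⁰ = 0.00195, above 0.0003. This test cannot cross at N=10.

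**Step 7: effect of conversion.** Cut-offs with the same nominal p on the t scale are 5.687 (9 df) and 2.036 (33 df), classical looks 10/34. Simulated error is 5.0%. Power for uncorrelated pairs goes from about 81% to 79%. With looks at 10, 34 and 75 the converted error is also 5.0%.

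**Step 8: chance of an efficacy stop at N=10 under the planned effect (10/34, classical, 1:1).**
- Known variance: drift 2,100 / (3,045 × √0.2) = 1.54, so P(Z > 3.616 − 1.54) = 1.9%.
- Unconverted paired t, uncorrelated pairs: 6.3%. If the within-pair correlation were 0.5 (an assumption; the documents give none): about 15%.
- Converted paired t: 0.6%.

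**The case against.** **Direct use of t is inferred.** The SAP nowhere says that a raw t is compared with the boundary. It leaves the mechanics to the software manual, and its mention of a Z scale could mean that a Z-scale statistic is intended. This stands: the defect is that the conversion is not stated, and the error rates apply only if none is made.

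**6.2% is the top of a range.** A reader might take it as the plan's error rate. The documents do not support that. SAP 3.5.5 calls N=34 an interim look, up to about 75 subjects are contemplated, and the signed-rank option shows no such inflation. The protocol expects overdispersed costs, so that branch may well be used.

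**The N=10 look is not the main cause.** A reader might blame the excess on it, or read it as contradicting the protocol. Step 5 answers the first point. On the second, the protocol delegates stopping methods to the SAP and itself refers to repeated interim analyses, so a further look is added detail that the protocol does not mention. Nor does the objection that the look unblinds the sponsor carry much weight, since Protocol 5.6 declares the study unblinded.

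**The look is not idle as written.** A reader might infer that it can hardly ever stop the trial. The 1.9% behind that view assumes known variance; the unconverted t that causes the inflation crosses in 6.3% of trials or more. The look becomes nearly inert only after conversion, or under the signed-rank test.

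**Conclusion.** The point holds as a gap in specification with a modest, calculable consequence. If the t-test branch is run without conversion, the two-sided error is about 5.2% to 6.2% instead of 5%. The upper end needs a 1:1 paired t and a last look at or near N=34. With 34 as the last look, the paired t falsely stops at N=10 in about 0.3% to 0.56% of null trials, against about 0.03% or less intended.

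These figures assume normal differences and only the named looks. They are not a bound for skewed costs: an assumed lognormal cost with the planned coefficient of variation (3,045/8,600 = 0.35) gives 6.2% at 1:1 and 6.6% at 4:1 for the paired t with looks 10/34. The 4.8% for the signed-rank test likewise needs symmetric differences. With four averaged controls under the same lognormal assumption it is 6.3%, which comes from asymmetry and is not cured by conversion.

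Whether to keep the N=10 look is a judgement for the sponsor. Once statistics are converted it adds no type I error, and it offers little chance of an early efficacy stop.

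**What to change.** 1. In SAP 3.5.5, state that at every look the t-test p-value, computed with its degrees of freedom, is converted to a signed normal score, and that this score is what SEQTEST compares with the boundary. State also the form in which a signed-rank result enters the comparison.
2. State whether the boundaries are classical O'Brien-Fleming or error spending, since SAP 3.3.5 and 3.5.4 can be read either way and the N=10 limit differs (3.616 or 3.971).
3. Make the protocol and SAP agree on whether an N=10 look is planned. If it is kept, say what it is for, given an efficacy stop in about 0.6% of trials after conversion under the planned effect, and none under the signed-rank test.

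Cost: SAP wording, a line of code, and a matching protocol sentence if the look stays. The planned 34 subjects need not change for this reason. Power falls by about two points (81% to 79%, looks at 10 and 34, uncorrelated pairs).

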3.5.6. Secondary Outcomes

Outcomes for the endpoints related to healthcare utilization (i.e., Secondary Endpoints 1-4) will be evaluated by appropriate statistical test dependent on the distribution of the outcome. Health-related quality of life outcomes will be evaluated for the Furoscix cohort only and will descriptively compare KCCQ-12 questionnaire responses at Day 0 versus Day 30. Change in BNP or NT-proBNP will be evaluated for the Furoscix cohort only and will descriptively compare values obtained at Day 0 versus Day 30. Subject and/or caregiver satisfaction with Furoscix Infusor will be descriptive.

3.6. Additional Analysis

3.6.1. Risk Factors

Risk factors associated with time (in days) to heart failure-related readmission to the emergency department and/or rehospitalization will be evaluated using Cox Proportional Hazards model. Application of the Efron approximation will be explored in order to account for tied observations. A stepwise selection process will be utilized to pare the model down. In this process, the single-term baseline variable with the highest p-value will be removed from the model until all factors have a $p < 0.10$. Baseline variables include those described in section 3.5.3 used for propensity score modeling in addition to the following variables: race, ethnicity, potassium supplements, heart failure type, NYHA classification, and baseline vital signs).

5. APPENDICES

Appendix A. Codebook for Claims Analysis

Appendix B. Case Report Form

5.1. Appendix A. Codebook for Claims Analysis

Claims
Codebook.pdf

5.2. Appendix B. Case Report Form

FREEDOM HF eCRF
